11.5.3. Adverse Events

All identified AEs are recorded and described on the appropriate AE page of the eCRF, except for those events occurring prior to the start of the screening period, which are recorded on the Medical History eCRF page. All Adverse Events (including non-TEAEs or AEs happening after End of Study Visit of the patient) recorded in the eCRF will be listed. All AEs summaries will be based on the safety population.

AE attributes that will be summarized into a new binary variable

- Relationship to study drug. If the AE is judged as Certainly Related, Probably Related, Possibly Related or if the relationship is Not Assessable/Unclassifiable then the AE will be judged as Related to the study drug.

The number and percentage of patients experiencing one or more AEs, as well as the number of events, will be summarized in the safety tables by cohort, relationship to study drug, and seriousness.

An overview of AEs will be provided with the number and percentage of patients reporting an event by cohort and by treatment group and overall. The summaries will be presented for the following categories:

- Any Serious AE
- Any Related AE
- Any Serious and Related AE
- Any AE by Relationship, Outcome, Intensity/Severity (Grade), Pattern

The number and percentage of patients experiencing one or more TEAEs will be summarized in the safety tables by cohort, relationship to study drug, seriousness,

intensity/severity and action taken.

An overview of TEAEs will be provided with the number and percentage of patients reporting a TEAE by cohort and by treatment group and overall. The summaries will be presented for the following categories:

- Any Serious TEAE
- Any Related TEAE
- Any Serious and Related TEAE
- Any TEAE by Relationship, Outcome, Intensity/Severity (Grade), Pattern, Action Taken

In addition, within each of the above categories, TEAEs will be further presented as follows:

- All TEAEs
- TEAEs by Grade
- TEAEs leading to drug interruption
- TEAEs leading to drug withdrawal
- TEAEs leading to dose modification (i.e. either dose reduction or dose increase)
- TEAEs leading to death

DLTs will be presented in a dedicated summary table.

AEs will be considered as related to study treatment if they are judged to be related to MEN1611 or to its combination (i.e. MEN1611 + Cetuximab).

The following information will be reported for all AE/TEAE listings: reported term, preferred term (PT) and system organ class (SOC), start and end date of the event, causality, intensity (grade), seriousness, pattern, outcome, action taken and report type (follow-up/initial).

In the listings, all AEs and their eventual follow-ups will be reported.

Whenever a patient experiences two or more AEs reported under the same Preferred Term and part of the same initial/follow up(s) group, these events will be counted as one. This will apply to all the AEs/TEAEs tables, except for those reporting the events stratified by action taken in which the TEAEs will be counted individually.

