8.6.1.4 Adverse Drug Reactions

Any untoward and unintended responses to an investigational medicinal product related to any dose administered. The definition covers also medication errors and uses outside what is foreseen in the protocol, including misuse and abuse of the product.

The definition implies a reasonable possibility of a causal relationship between the event and MEN1611, cetuximab or both given in combination. This means that there are facts (evidence) or arguments to suggest a causal relationship.

ADRs are considered all AEs for which the relationship with any of the IMPs is considered as:

1. Certainly related
2. Probably related
3. Possibly related
4. Unassessable/Unclassifiable

AEs are not considered as ADRs when the relationship is judged as:

1. Unlikely related
2. Not related

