8.6.4 Management of Non-Serious Adverse Events and/or Laboratory Abnormalities

The Investigator must record all the available information concerning any non-serious AE (whether or not deemed related to MEN1611, to cetuximab or to their combination) in the corresponding section of the eCRF, eCRF-AE pages, **within 5 calendar days** after the first knowledge of the occurrence of the event.

When the site personnel enter a new AE/case in the eCRF, an automatic alert notification will be generated and sent to the Sponsor's SDSM.

If relevant, all eCRF pages concerning medical history, concomitant medication, laboratory tests and any other relevant information will also be retrieved by the Sponsor's SDSM and saved in the safety master file.

Any further significant information and supporting documentation that become available (such as copies of laboratory tests, procedures, etc.) shall also be provided by the Investigator through the eCRF or by e-mail in case of eCRF unavailability to the Sponsor's SDSM.

In addition, during the clinical study, abnormalities in laboratory analyses, physical examination, urinalysis, vital signs and 12-lead ECG (newly occurring after ICF signature or worsening of previously known abnormalities), which are considered clinically relevant by the Principal Investigator (such as values significantly above or under normal range or which require an

intervention or diagnostic tests, or may result in the discontinuation of the study treatment), should be reported as AEs. All clinically significant abnormalities in laboratory values, physical examination, urinalysis, vital signs and 12-lead ECG will be collected and reviewed by the Sponsor on a bi-monthly basis.

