9.3.4 Safety Analysis

Safety analysis will be performed on the safety population through descriptive statistics during each study phase. Summary statistics will report the incidence of the AEs by CTCAE toxicity Grade, dose level, relationship to study treatment and overall. Counts and percentages will be reported for the results of ECG, laboratory values, vital signs, physical examination, all classified as normal/abnormal not clinically significant/abnormal clinically significant by dose level and visit.

Descriptive statistics will also be produced for the extent of exposure, overall drug administration, drug administration by dose level and dose delay by dose level.

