3.1. Changes from study protocol

All analyses detailed in this document are as specified in the protocol and subsequent amendments, no major changes from the protocol-planned primary analysis have been performed. The only exception is the PK data analysis, for which no estimation of individual PK parameters will be conducted by using a population PK approach. Plasma concentrations of MEN1611 by time-point will be summarised by descriptive statistics only.

4. Study overview

MEN1611 is a potent and selective Class I PI3K inhibitor with a novel structure. In particular, it has potent inhibitory activities against Class I PI3K α . MEN1611 is yellow to greenish yellow powder or powder with lumps, stable in the solid state. The MEN1611 drug product is a hard capsule for oral administration.

This study is designed as an Open-label, Multicenter, Phase Ib/II Study of MEN1611 and Cetuximab, to be conducted in approximately 29 sites in Europe and US.

Phosphatidylinositol 3-kinase, catalytic, alpha polypeptide gene (PIK3CA) mutated, N-K-RAS and BRAF wild type, metastatic colorectal cancer, in patients failing irinotecan, oxaliplatin, 5-FU and anti- epidermal growth factor receptor (EGFR) containing regimens will be enrolled.

The study is aimed to determine the RP2D of MEN1611 when administered orally in combination with cetuximab during the first step of the study, and to assess the anti-tumor activity of MEN1611 in combination with cetuximab during the second step.

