7.2.2. Key definitions

Baseline values

The baseline value of an assessment is defined as the value measured before the first study drug administration at Visit 1 of Cycle 1. If the pre-infusion value at Visit 1 is missing or not done, the value measured during the Screening Visit is considered as baseline value.

Adverse Events (AEs)

Any untoward medical occurrence in a patient or clinical study patient administered a medicinal product and which does not necessarily have a causal relationship with this treatment. An AE can therefore be any unfavourable and unintended sign (including an abnormal laboratory finding), symptom, or disease temporally associated with the use of a medicinal product, whether or not considered related to the medicinal product.

Treatment-Emergent Adverse Events (TEAEs)

If an AE occurs for the first time or if it worsens in terms of seriousness or severity after the first study treatment (either MEN1611 or cetuximab) intake, it will be classified as TEAE, otherwise it will be classified as non-TEAE.

AEs that have missing onset dates will be considered to be treatment-emergent, unless the stop date is known to be prior to the first administration of the study medication.

Adverse Drug Reactions (ADRs)

An adverse drug reaction (ADR) in this study is defined as any adverse event (AE) suspected by the Investigator and/or the Sponsor to be related to MEN1611, cetuximab or both given in combination. Toxicities will be graded according to the NCI CTCAE v5.0, except for segmental wall-motion abnormalities (not described in NCI CTCAE v5.0).

All AEs (including SAEs) are to be accurately recorded on the AE page of the patient's eCRF. Each event will be graded for severity using the classifications of NCI CTCAE v5.0. For events not addressed in the NCI CTCAE v5.0 classification, the following grading will apply:

- **Mild (Grade 1)** - Mild; asymptomatic or mild symptoms; clinical or diagnostic observations only; intervention not indicated;
- **Moderate (Grade 2)** - Moderate; minimal, local or noninvasive intervention indicated; limiting age-appropriate instrumental activity of daily living;
- **Severe (Grade 3)** - Severe or medically significant but not immediately life-threatening; hospitalization or prolongation of hospitalization indicated; disabling; limiting self-care activity of daily living;
- **Life-threatening (Grade 4)** - Life-threatening consequences; urgent intervention indicated.

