- **Death (Grade 5)** - Related to adverse event.

NOTE: In case of an AE/ADR consisting of a laboratory abnormality, its intensity (severity) should be ranged based on the level of abnormality of the out-of-range value and/or its interference on patient ability to perform daily routine activities, as above defined. A severe AE, as defined by the above grading scale, is NOT the same as serious AE.

Serious Adverse Event (SAE) / Serious Unexpected Adverse Reaction (SUSAR)

Any SAE judged by the Investigator or the Sponsor as drug-related and considered as unexpected is qualified as a Suspected Unexpected Serious Adverse Reaction (SUSAR). SUSARs are subject to expedited reporting, as having a “Reasonable Possibility” of relationship with the study treatment (MEN1611, cetuximab or their combination).

Any untoward medical occurrence or effect that at any dose:

- results in death.
- is life-threatening.

Note: the term life-threatening in the definition of “serious” refers to an event in which the patient was at risk of death at the time of the event; it does not refer to an event which hypothetically might have caused death if it were more severe.

- requires patient hospitalization or prolongation of existing hospitalization.
- results in persistent or significant disability/incapacity.
- is a congenital anomaly/birth defect.
- is an ‘important medical event’ that may jeopardize the patient or may require an intervention to prevent one of the above characteristics/consequences.

Note: Hospitalization lasting less than 24 hours or pre-planned hospitalization for medical intervention, such as chemotherapy administration, shall not qualify as SAE.

Any other AE/ADR which is not included in the above definitions will be considered as non-serious. The Investigator should also promptly report all the SAEs to the Sponsor’s Drug Safety Manager.

Algorithm for Causality Assessment of Adverse Events

The relationship between an AE and study treatments will be judged according to the following categories:

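### SAP 11.5.3, read naturally, leaves adverse events attributed to cetuximab alone out of 'related to study treatment', against the SAP's own ADR and SUSAR wording and the protocol, so the Related tables may understate the combination's related events

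*SAP*

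**What the plan says.** The rule is the last sentence on summaries in SAP 11.5.3: "AEs will be considered as related to study treatment if they are judged to be related to MEN1611 or to its combination". A parenthesis then explains the combination as MEN1611 plus cetuximab. Two attributions are named, and cetuximab alone is not one of them.

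The same section also builds a binary variable: certain, probable, possible and unassessable ratings all become related to the study drug. It groups causality categories and does not say which product counts.

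Elsewhere the SAP is wider. In 7.2.2 an ADR is an event "suspected by the Investigator and/or the Sponsor to be related to MEN1611, cetuximab or both given in combination", and the SUSAR text speaks of a "relationship with the study treatment (MEN1611, cetuximab or their combination". The protocol matches this. Section 8.6.1.4 refers to "a causal relationship between the event and MEN1611, cetuximab or both given in combination", 8.6.1.7 uses the same three-way wording, and 8.6.4 asks sites to record non-serious events "whether or not deemed related to MEN1611, to cetuximab or to their combination".

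For the analysis itself, Protocol 9.3.4 says: "Summary statistics will report the incidence of the AEs by CTCAE toxicity Grade, dose level, relationship to study treatment and overall". It gives no narrower meaning. On departures from the protocol, SAP 3.1 says: "The only exception is the PK data analysis".

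**The concern.** The secondary safety objective (Protocol 7.2) concerns MEN1611 given together with cetuximab, and both drugs are study treatment. A reader of a table headed Related will assume the meaning in the ADR definition, which is an event related to either drug or to both. Under 11.5.3 as written, an event attributed only to cetuximab does not qualify.

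Such events are foreseeable from the plan's own schedule. On Day 1 of Cycle 1 (Protocol 8.5.1) the order is premedication, a 120-minute cetuximab infusion, then the first MEN1611 dose. A reaction during that infusion comes before any MEN1611, so timing gives no ground for attributing it to MEN1611 or to the pair. If the patient then takes MEN1611, the patient is in the safety population (SAP 7.3) and the event is a TEAE (SAP 7.2.2), yet it falls outside the Related tables. Protocol 8.4.5 ends cetuximab permanently after a severe infusion reaction, so such an event could also be missing from Table 2.4.3.2, the related TEAEs that led to drug withdrawal.

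At stake is the related-event profile reported for the regimen, which could look better than the plan's own ADR definition would show.

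**Working it through.** The plan states no figure to reproduce. The check compares definitions, counts outputs and adds one illustration of scale.

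**1. Which attributions count**

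| Place | MEN1611 | Combination | Cetuximab alone |
|---|---|---|---|
| SAP 11.5.3, related to study treatment | yes | yes | not named |
| SAP 7.2.2, ADR | yes | yes | yes |
| SAP 7.2.2, SUSAR | yes | yes | yes |
| Protocol synopsis, ADR | yes | yes | yes |
| Protocol 8.6.1.4, ADR (any of the IMPs) | yes | yes | yes |
| Protocol 8.6.1.7, SUSAR | yes | yes | yes |
| Protocol 8.6.4, recording of non-serious AEs | yes | yes | yes |

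The four categories that 11.5.3 groups as related are the same four that make an ADR in SAP 7.2.2. The two definitions therefore agree on strength of causality and differ only on product.

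The TEAE definition ("after the first study treatment (either MEN1611 or cetuximab) intake, it will be classified as TEAE") supports the wider meaning of study treatment. It concerns timing, so it does not itself conflict with a relatedness rule.

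**2. Outputs that use the related flag (SAP 13.2.1 and 13.2.2)**

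- Related or Serious-and-Related tables: 2 of the 3 numbered 2.2.2, plus 6 numbered 2.4.x (2.4.1, 2.4.2, 2.4.3.1, 2.4.3.2, 2.4.4.3, 2.4.4.4), plus 6 numbered 2.6.x (2.6.1, 2.6.2, 2.6.3.1 to 2.6.3.4) = 14. These include grade, withdrawal and death versions.
- Tables without the flag: 2.2.1 (1), the serious table numbered 2.2.2 (1), 2.3.1 and 2.3.2 (2), 2.3.3.1 to 2.3.3.4 (4), and the 2.5.x set (6) = 14.
- Overviews 2.2 and 2.3 = 2; only their related rows are touched.
- Total 14 + 14 + 2 = 30, not counting DLT Table 2.7.
- Listings: 5.12 and 5.14, which is 2 of the 5 from 5.10 to 5.14.

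No table is titled as cetuximab-related or MEN1611-related.

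**3. Scale (illustration only)**

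Inputs: n = 40, the efficacy-evaluable target in the synopsis (the safety population may be larger); infusion reactions in more than 10% of patients (mild to moderate) and more than 1% (severe), from Protocol 8.4.5; skin reactions in more than 80%, from 8.4.6. The lower bounds are used. Let f be the share attributed to cetuximab alone. The documents do not give f, so it is run from 0 to 1.

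- Mild to moderate infusion reactions: 40 × 0.10 = 4 expected; P(at least one) = 1 − 0.90^40 = 0.985. Dropped from related counts: 4f, that is 0, 1, 2, 3, 4 at f = 0, 0.25, 0.5, 0.75, 1.
- Severe infusion reactions: 40 × 0.01 = 0.4 expected; P(at least one) = 1 − 0.99^40 = 0.331. Dropped: 0.4f.
- Skin reactions: 40 × 0.80 = 32 expected. Dropped: 32f, that is 0, 8, 16, 24, 32 at the same values.

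Under the ADR wording none are dropped. The infusion rates cover reactions at any infusion, not only the first.

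**The case against.** The sentence in 11.5.3 says 'if', not 'only if', and the combination could be read loosely as the whole regimen. This is fair: the exclusion is an inference. It is still the natural reading, because the parenthesis defines the combination as the two drugs together and both documents elsewhere list cetuximab as a separate option. A programmer following the sentence has no basis for flagging a cetuximab-only event.

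The rule may be a deliberate MEN1611-centred choice. The safety population is also defined by MEN1611 intake, and Protocol 9.3.4 does not define relationship by product. That could be legitimate, but nothing declares it and no title says so. The SAP cites Protocol 4.0 while the protocol at hand is 5.0, so the lack of a declaration is judged against a version the SAP does not name. The conflict inside the SAP does not depend on version.

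Several limits stand. Possible and unassessable ratings count as related, so an event drops out only if it is rated unlikely or not related to MEN1611 and is not attributed to the combination. Overlapping toxicity makes this less likely for some terms: at 48 mg BID in the breast cancer study, 57.14% of patients had skin TEAEs and 66.1% had diarrhoea. Those figures are regardless of causality, and the patients also received trastuzumab with or without fulvestrant, so they show overlap and not attribution. The overview rows by relationship may show part of the missing information. Safety analysis is descriptive, and dose selection rests on DLTs and committee review of all safety data.

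A reader might infer that cetuximab toxicity disappears from the report. It does not: the all-causality and serious tables (2.2.1, the serious 2.2.2, 2.3.x, 2.5.x), the general listings, which show causality, the DLT table and SUSAR reporting are unaffected.

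**Conclusion.** The point holds as a conflict of definitions with a foreseeable effect on the tables. Read naturally, SAP 11.5.3 leaves cetuximab-only events out of related to study treatment. This contradicts the ADR and SUSAR wording in SAP 7.2.2 and the protocol, and SAP 3.1 does not declare it. Followed as written, it affects 14 tables, the related rows of 2 overviews and 2 listings.

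The effect on patient counts is unknown and runs from zero upward. A reader might take the illustration as an estimate of the shortfall, but the documents do not support that, because f is not given. Nor do they support treating the TEAE definition as a second contradiction.

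The conclusion assumes that the sentence is applied literally and that the eCRF can record an attribution to cetuximab alone. Protocol 8.6.4 suggests that it can, but the eCRF is not in the documents. The correction should be made before the tables are programmed, since the remedy is cheap and the labels would otherwise mislead.

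**What to change.** In SAP 11.5.3, replace the sentence with: related means a causality rating of certain, probable, possible or unassessable to MEN1611, to cetuximab or to their combination. Apply it to the Related and the Serious-and-Related tables numbered 2.2.2, to 2.4.x and 2.6.x, to the related rows of Tables 2.2 and 2.3, and to Listings 5.12 and 5.14. Add a MEN1611-related column (MEN1611 or combination) to the 14 tables and to the 2 overviews, 16 in all, so that the MEN1611-centred view is kept.

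If the narrower rule is intended, declare it in SAP 3.1 and title the affected tables and listings 'MEN1611-related'.

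The cost is one sentence and one column, with slightly more programming. Related-event percentages will be equal or higher. New data should not be needed, because the present rule already requires causality by product. That is an inference, to be confirmed against the eCRF.

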11.5.4. Vital Signs

Descriptive statistics for Vital Signs results (Systolic and Diastolic Blood Pressure, Heart Rate, Height, Respiratory Rate, Temperature, Heart Rate, Weight) by cohort and Visit will be provided in the TLFs, both in terms of absolute values and change from baseline.

Also frequencies and percentages for the investigator judgements, calculated considering the patients who have performed the examination at each visit, are reported.

11.5.5. Physical Examination

A summary table of Physical Examination parameters by cohort and visit will be provided in the TLFs. Percentages are calculated considering the patients who have performed the examination.

11.5.6. 12-ECG

Summary tables of 12-lead ECG parameters and interpretation and ECOG performance status by cohort and visit will be provided in the TLFs, both in terms of absolute values and change / shift from baseline.

In these tables the frequencies and percentages, calculated considering the patients who have performed the examination at each visit, are reported.

11.5.7. Safety laboratory tests

An overall summary table of hematology, biochemistry, coagulation and urinalysis parameters by cohort and visit will be provided in the TLFs, both in terms of absolute values and change from baseline.

Percentages are calculated considering the patients who have performed the examination.

Also frequencies and percentages for the investigator judgements, calculated considering the patients who have performed the examination at each visit, are reported.

12. Efficacy evaluations

Efficacy analysis will be performed only through descriptive statistics, no formal hypothesis testing will be performed.

12.1. Efficacy analysis

The following parameters will be summarized by cohort and overall (if appropriate) on the Efficacy population:

- Best Overall Response
- Disease Control Rate
- Objective Response Rate
- Duration of response (DoR)
- Progression Free survival (PFS);
- Overall Survival (OS).

ORR locally assessed is the primary endpoint of the Cohort Expansion Phase. All efficacy

endpoints related to tumour assessment will be evaluated considering both local (secondary endpoints) and central (exploratory endpoints) radiology assessments.

Best Overall Response (BOR) is derived as follows:

- If a subject has at least one overall response of CR, then BOR is CR;
- If a subject doesn't have any overall response of CR but has at least one overall response of PR, then BOR is PR;
- If a subject doesn't have any overall response of CR or PR but has at least one overall response of SD (or Non-CR / Non-PD) at least six weeks after the first intake of MEN1611, then BOR is SD (or Non CR / Non PD);
- If a subject doesn't have any overall response of CR, PR, SD (or Non-CR / Non-PD) after at least 6 weeks from the first intake of MEN1611, but has at least one overall response of PD, then BOR is PD;
- In all other cases, BOR is NE.

Objective Response Rate (ORR) is calculated as the sum of BOR rates of complete response (CR), partial response (PR).

Disease Control Rate (DCR) is calculated as the sum of BOR rates of complete response (CR), partial response (PR) and stable disease (SD).

Overall Survival (OS) is calculated as:

- In case of all-cause death:
OS = date of death - date of first study treatment administration + 1;
- In case of censored information not for drop-out:
OS = date of end of observation period (i.e. maximum between end of study and last follow up date) - date of first study treatment administration + 1;
- In case of censored information for drop-out:
OS = last available date in eCRF - date of first study treatment administration + 1.

Progression-free Survival (PFS) is calculated as:

- In case of death/disease progression:
PFS = date of death or date of first disease progression - date of first study treatment administration + 1
For subjects who experienced both death and progression disease, the date referred to the event that came first is considered.
- In case of censored information due to responding subjects or lost to follow-up:
PFS = date of censoring - date of first study treatment administration + 1

Detailed censoring rules are as follows:

Circumstances		Options for end-date (progression or censoring)	Outcome
1	Documented Progression	(i) Date of documented progression	Progressed
2	Death without documented progression	(i) Date of death	Progressed
3	Documented progression or death after exactly one missing assessment	(i) Date of progression or death	Progressed
4	Documented progression or death after two or more missing assessments	(i) Date of last adequate assessment ^a	Censored
5	No documented progression and no death (with at least one post baseline assessment)	(i) Date of last adequate assessment	Censored
6	Treatment discontinuation Reason ' Disease progression/clinical progression/progression ' without radiological assessment.	(i) Ignore clinical progression and follow situations above	As per above circumstances
7	No baseline tumor assessment	Date of first study treatment administration	Censored
8	No post baseline assessment and no death	Date of first study treatment administration	Censored
9	Subject lost to follow-up (or withdrew consent) before documented progression or death	(i) Date of last adequate assessment	Censored

^aAfter the last adequate tumor assessment. Date of next scheduled assessment- as specified in the protocol

Duration of Response (DR) is calculated as:

- In case of disease progression:
DR = date of disease progression – date of first occurrence of a BOR of PR, CR or SD + 1
- In case of censored information:
DR = date of last tumor assessment – date of first occurrence of a BOR of PR, CR or SD + 1

Note: subjects with only one assessment post baseline with response equal to PD won't be counted for the DR calculation

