11.2. Descriptive statistics

All study variables (with the exception of PK variables) will be presented by dose cohort and

overall, using the appropriate descriptive statistics according to the variable nature, unless otherwise specified:

- **Continuous variables:** Number of non-missing observations, arithmetic mean, standard deviation, minimum, median and maximum.
- **Categorical variables:** Number of non-missing observations and column percentages (N, %).
- **Time to event variables:** Number of non-missing observations, number and percentage of censored observations, 1st quartile, median (and its 95% CI), 3rd quartile, Kaplan-Meier survival curves and event rate every 28 days.

The behaviour over time of study variables will be summarised by treatment cohort and overall as follows:

- **Continuous variables:** Descriptive statistics for each time point and for the absolute/percentage differences to baseline.
- **Categorical variables:** Descriptive statistics for each time point and shift tables to baseline.

Correlation among patient's variables will be evaluated calculating the appropriate correlation coefficient with the respective statistical significance level.

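### The primary response rate is planned without a confidence interval, and the best-overall-response rule does not stop at first progression (the latter mainly affects the central read)

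*SAP*

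**What the plan says.** **Summary of the primary endpoint.** SAP 12.1 states that "ORR locally assessed is the primary endpoint of the Cohort Expansion Phase" and defines ORR as the sum of the CR and PR rates from BOR, summarised on the Efficacy population. SAP 12 and protocol 9.3.3 make the efficacy analysis descriptive, and SAP 12 adds that nothing will be formally tested. The summary format comes from SAP 11.2, which repeats protocol 9.3.1. Its entry for categorical variables begins "Number of non-missing observations and column percentages (N" and, apart from the percent sign that closes the bracket, ends there. Time-to-event variables get "1st quartile, median (and its 95% CI), 3rd quartile, Kaplan-Meier survival curves" among other statistics. Neither SAP 12.1 nor the titles of Tables 3.1.1 to 3.2.2 in SAP 13.2 add an interval for ORR.

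**BOR.** The SAP 12.1 rule is a hierarchy over all assessments:

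- It opens with "If a subject has at least one overall response of CR, then BOR is CR".
- Without a CR, any PR gives PR.
- Without either, BOR is SD if the patient "has at least one overall response of SD (or Non-CR / Non-PD) at least six weeks after the first intake of MEN1611".
- PD applies only if none of these is met.

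No step limits the assessments to those up to progression.

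**PFS and duration of response.** The PFS event date in the same section is "date of death or date of first disease progression". Duration of response runs from the "date of first occurrence of a BOR of PR, CR or SD + 1" (the + 1 is the day adjustment) to a progression date that is not specified as the first. The only exclusion is for "subjects with only one assessment post baseline with response equal to PD". SAP 12.1 applies all tumour endpoints to both the local read and the exploratory central read.

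**The concern.** The Step 2 primary result is a single proportion in, according to the synopsis (Study Duration), up to 40 evaluable patients. With no test, an interval is the only way the report can show how uncertain that proportion is. The plan gives intervals to secondary time-to-event medians and, in protocol 9.3.2, to PK means, but not to the primary endpoint. No formal comparator is named, so the point concerns precision only.

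The BOR rule raises a different problem. A patient read as PD and then as PR or SD has a PFS event at the first scan and is still counted in ORR or DCR from the second. The duration-of-response exclusion does not catch this patient, who has two post-baseline assessments. The by-timepoint Tables 3.2.1 and 3.2.2 and the response listings would show the sequence but would not correct BOR, ORR or DCR.

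A smaller mismatch sits beside this. Protocol 8.5.5.2 (v5.0) starts duration of response at confirmation of response, while SAP 5.4.2 and 12.1 start it at first occurrence. The SAP says it reflects protocol v4.0, so this is a wording difference to reconcile and not evidence of an undisclosed change.

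**Working it through.** **No stated precision to reproduce.** Protocol 9.1 and SAP 8 (sample size) are redacted or blank in the public versions, so there is no planned power or interval width to check. The calculations below are illustrations.

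**1. Width of the missing interval.** Input: n up to 40 (synopsis, Study Duration), with 35 and 30 as assumed smaller values. For x responders in n, the exact Clopper-Pearson 95% limits are

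- lower = Beta(0.025; x, n − x + 1)
- upper = Beta(0.975; x + 1, n − x)

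| x/n | Rate | Exact 95% CI | Width (points, from unrounded limits) |
|---|---|---|---|
| 4/40 | 10% | 2.8% to 23.7% | 20.9 |
| 8/40 | 20% | 9.1% to 35.6% | 26.6 |
| 12/40 | 30% | 16.6% to 46.5% | 30.0 |
| 16/40 | 40% | 24.9% to 56.7% | 31.8 |
| 7/35 | 20% | 8.4% to 36.9% | 28.5 |
| 6/30 | 20% | 7.7% to 38.6% | 30.9 |

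A DCR of 20/40 = 50% would have limits of 33.8% to 66.2%.

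**2. The BOR rule applied to read sequences.** Each sequence is classified by SAP 12.1 as written, then by the same rule using only assessments up to and including the first PD.

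| Reads (weeks 8, 16, 24) | SAP BOR | BOR cut at first PD | PFS event |
|---|---|---|---|
| PD, PR | PR | PD | week 8 |
| PD, SD | SD | PD | week 8 |
| SD, PD, PR | PR | SD | week 16 |
| PR, PD | PR | PR | week 16 |

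Only a better read after PD changes the result. The ordinary sequence of response then progression is unaffected.

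**3. Effect on duration of response.** With 28-day cycles and scans at Cycle 3 Day 1 and Cycle 5 Day 1, the nominal scan days are 1 + 2×28 = 57 and 1 + 4×28 = 113. The first scan, with its 7-day window, falls on days 50 to 57, after the 42-day minimum for SD. For PD on day 57 and PR or SD on day 113:

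- PFS = 57 − 1 + 1 = 57 days.
- Duration of response = 57 − 113 + 1 = −55 days, if the first PD date is used. Across the 7-day scan windows the range is 50 − 113 + 1 = −62 to 57 − 106 + 1 = −48. The +5-day visit window is not included.
- If a later PD date is used, the duration is not negative, but it begins 113 − 57 = 56 days after the patient's PFS event.

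**4. Effect on the rates.** One reclassified patient in 40 is 1/40 = 2.5 points of DCR, and of ORR when the later read is PR.

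**5. Where such sequences can arise.**

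- *Local read:* disease progression ends treatment (protocol 8.2.3.2) and scheduled scans run until RECIST progression or the End of Study Visit (8.5.5.2). Other anticancer therapy is not allowed during the study (8.4.8). A local read after local PD should be very rare.
- *Central read:* protocol 8.5.1 makes it retrospective, so a central PD does not stop treatment or scanning, and later scans can exist.

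**The case against.** On the interval, the other side has three arguments. The redacted sample-size and Step 2 design text may hold a precision statement. SAP 11.2 applies unless something else is specified, and the table shells are not visible. An exact interval can also be computed by any reader from the count and percentage, so no information is lost and no estimate is biased. The first two are fair limits and are why this point is confined to the visible sections. The third is true but does not explain why the plan gives secondary medians an interval and leaves readers to work out the primary one. Being descriptive is no reason to omit it, since those medians are descriptive too.

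On the BOR rule, the primary local ORR is almost untouched. What remains is an exploratory read that needs a PD called centrally but not locally, followed by a better central read. The BIRC applies RECIST 1.1, and its Charter may stop reading at first PD. All of this stands, and it limits the size of the problem. It does not repair the SAP rule, which as written would classify such a patient wrongly.

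The negative duration depends on using the first PD date. SAP 12.1 says first only for PFS, and SAP 5.4.2 can be read as meaning a progression after the response. That is correct, so −55 days is conditional. On the alternative reading, duration of response starts after the same patient's PFS event, so the contradiction with PFS remains.

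The confirmation versus first-occurrence mismatch is minor and adds little weight.

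**Conclusion.** The point holds and should be fixed, though it does not threaten the validity of the local primary estimate. In the visible plan the primary ORR has no measure of precision. At n = 40 the unreported 95% interval is about 21 points wide at an observed 10% and 32 points wide at 40%, and it is wider if fewer than 40 patients are evaluable. The observed rates used here are illustrative.

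The BOR rule is inconsistent with the PFS rule in the same section. The effect on local ORR should be close to nil. On the central read it is 2.5 points per affected patient in 40, with a frequency that the documents do not allow anyone to estimate.

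Confidence is moderate, because the redacted sample-size and design text could contain a precision statement and the BIRC Charter could already stop the central read at first PD.

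**What to change.** 1. In SAP 12.1, report ORR and DCR, local and central, with exact Clopper-Pearson 95% CIs.
2. Derive BOR only from assessments up to and including the first PD by the same reader, or before the start of new anticancer therapy, whichever comes first. State that duration of response uses the same first PD date as PFS.
3. Reconcile the start of duration of response between protocol 8.5.5.2 and SAP 5.4.2 and 12.1.

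Optionally, keep the single-reading ORR as primary, which is a stated choice, and add a supportive rate of responses maintained at the next scheduled scan. Scans are about 8 weeks apart, so that rate also tests durability. The number of responders with no later scan should be given with it.

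The cost is SAP wording and programming, with no new scans or data. Item 1 leaves the primary endpoint and its derivation unchanged. For item 2, the sponsor should check whether protocol 9.5 treats it as a change to the primary analysis, which would call for a substantial amendment, even though it should rarely alter the local ORR.
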